## SYNOPSIS

Title:	A Randomized, Controlled Double-blind Study Comparing the Efficacy and Safety of Orelvo (voclosporin) (23.7 mg Twice Daily) with Placebo in Achieving Renal Response in Subjects with Active Lupus Nephritis.
Short Title:	AURORA (AURinia Orelvo Renal Assessments) 1: Aurinia Renal Response in Active Lupus with Voclosporin
Study Product:	Orelvo (voclosporin)
Indication:	Active lupus nephritis
Phase:	3
Sponsor:	Aurinia Pharmaceuticals Inc.
Study Code:	AUR-VCS-2016-01
Objectives:	
Primary Objective:
 
 
• To assess the efficacy of Orelvo (voclosporin) compared with placebo in achieving renal response after 52 weeks of therapy in subjects with active lupus nephritis (LN)
 
 
Secondary Objective:
 
 
• To assess the safety and tolerability of Orelvo over 52 weeks compared with placebo in subjects with active LN
 

Design:	Prospective, randomized, placebo-controlled, double-blind, parallel-group, 52-week, international, multicenter, 2-arm comparison study of Orelvo versus matching placebo.
Treatment:	
Investigational Treatment:
 
Orelvo softgel capsules containing 7.9 mg drug. Approximately 324 subjects will be randomized to Orelvo (23.7 mg twice daily (BID)) or matching placebo (162 subjects per arm).
 
All subjects will receive an initial treatment of intravenous (IV) methylprednisolone, followed by a reducing taper of oral corticosteroid. Additionally, all subjects will receive background therapy with mycophenolate mofetil (MMF).
 
All subjects who complete participation and study treatment through 52 weeks and provide consent will have the opportunity to enroll into a continuation study (design pending finalization).

Inclusion Criteria:	
 
1. Written informed consent before any study-specific procedures are performed.
 
2. Male or female subjects with a minimum age of 18 (or legal age of consent if >18 years) to 75 years of age, inclusive, at the time of screening (Visit 1).
 
3. Previous diagnosis of systemic lupus erythematosus (SLE) according to the American College of Rheumatology criteria (1997; see Appendix 5).
 

	
4. Subjects with evidence of active nephritis, defined as follows:
 
Kidney biopsy result within 2 years prior to screening indicating Class III, IV-S, IV-G (alone or in combination with Class V), or Class V LN (see Appendix 3) with a doubling or greater increase of urine protein creatinine ratio (UPCR) within the last 6 months to a minimum of <math>\geq 1.5</math> mg/mg for Class III/IV or to a minimum of <math>\geq 2</math> mg/mg for Class V at screening. Biopsy results over 6 months prior to screening must be reviewed with a medical monitor to confirm eligibility.
 
OR
 
Kidney biopsy result within 6 months prior to screening indicating Class III, IV-S, or IV-G (alone or in combination with Class V) LN with a UPCR of <math>\geq 1.5</math> mg/mg at screening.
 
OR
 
Kidney biopsy result within 6 months prior to screening indicating Class V LN and a UPCR of <math>\geq 2</math> mg/mg at screening.
 
A biopsy can be performed during screening, if not available. The above criteria must be fulfilled at baseline.
 
5. In the opinion of the Investigator, subject requires high-dose corticosteroids and immunosuppressive therapy.
 
6. Subject is willing to take oral MMF for the duration of the study, either by continuing current MMF therapy or by initiating it on or before the Baseline Visit.
 
7. Women of childbearing potential must have a negative serum pregnancy test at screening and a negative urine pregnancy test at baseline. Two effective forms of contraception must be used simultaneously unless abstinence is the chosen method. Subjects must use effective contraception during the study (see Section 5.4, Adequate/Effective Contraception).

Exclusion Criteria:	
1. Subjects unable or unwilling to give written informed consent and/or to comply with study procedures.
 
2. Estimated glomerular filtration rate (eGFR) as calculated by the Chronic Kidney Disease Epidemiology Collaboration equation of <math>\leq 45</math> mL/minute/1.73 m^2 at screening confirmed before randomization.
 
3. Currently taking or known need for any of the medications listed in Section 7.8, Prohibited Therapy and Concomitant Treatment at screening or during the study. This includes prohibited medications prior to screening as specified in Section 7.8.1, Prohibited Medications.
 
4. Currently requiring renal dialysis (hemodialysis or peritoneal dialysis) or expected to require dialysis during the study period.
 
5. A previous kidney transplant or planned transplant within study treatment period.

- 
6. Any known hypersensitivity or contraindication to MMF, mycophenolic acid, cyclosporine, corticosteroids or any components of these drug products.
  7. Current or medical history of:
    - Congenital or acquired immunodeficiency.
    - In the opinion of the Investigator, clinically significant drug or alcohol abuse within 2 years prior to screening.
    - Malignancy within 5 years of screening, with the exception of basal and squamous cell carcinomas treated by complete excision. Subjects with cervical dysplasia that is cervical intraepithelial neoplasia 1, but have been treated with conization or loop electrosurgical excision procedure and have had a normal repeat Papanicolaou test are allowed.
    - Lymphoproliferative disease or previous total lymphoid irradiation.
    - Severe viral infection (e.g., cytomegalovirus, hepatitis B virus, hepatitis C virus) within 3 months of screening; or known HIV infection. Severe viral infection is defined as active disease requiring antiviral therapy.
    - Active tuberculosis (TB), or known history of TB/evidence of old TB if not taking prophylaxis with isoniazid (see Section 9.2.1, [Screening Visit Procedures](#)).
  8. Other known clinically significant active medical conditions, such as:
    - Severe cardiovascular disease including congestive heart failure, history of cardiac dysrhythmia or congenital long QT syndrome. QT interval duration corrected for heart rate using method of Fridericia exceeding 480 msec in the presence of a normal QRS interval (<110 msec) at time of screening will result in exclusion.
    - Liver dysfunction (aspartate aminotransferase, alanine aminotransferase, or bilirubin  $\geq 2.5$  times the upper limit of normal) at screening and, if abnormal at screening, then confirmed that the levels have returned to <2.5 times upper limit of normal before randomization.
    - Chronic obstructive pulmonary disease or asthma requiring oral steroids.
    - Bone marrow insufficiency unrelated to active SLE (according to Investigator judgment) with white blood cell count <2,500/mm^3; absolute neutrophil count <1.3  $\times 10^3/\mu\text{L}$ ; thrombocytopenia (platelet count <50,000/mm^3).
    - Active bleeding disorders.
    - Current infection requiring IV antibiotics.
  9. Any overlapping autoimmune condition for which the condition or the treatment of the condition may affect the study assessments or outcomes (e.g., scleroderma with significant pulmonary hypertension; any condition for which additional immunosuppression is indicated). Overlapping conditions for which the condition or treatment is not expected to affect assessments or outcomes (e.g., Sjögren's syndrome) are not excluded.
-

[figure not shown]

	
10. No vaccines using live organisms, virus or bacterial, are allowed during screening and while taking the study treatment.
 
11. Other major physical or psychiatric illness or major traumatic injury within 6 months prior to screening that may affect study conduct or interfere with study assessments or outcome.
 
12. Any other medical condition which, in the Investigator’s judgment, may be associated with increased risk to the subject or may interfere with study assessments or outcomes.
 
13. Subjects who are pregnant, breast feeding or, if of childbearing potential, not using adequate contraceptive precautions.
 
14. Participation in another interventional clinical study within 4 weeks prior to screening and/or receipt of investigational drugs within 4 weeks or 5 half-lives of the drug (whichever is longer) prior to screening.
 
15. Subjects randomized and treated in a previous voclosporin clinical study.


Primary Endpoint:
	
Renal response at Week 52 will be adjudicated by the Clinical Endpoints Committee based on the following parameters:
 
 
• UPCR of <math>\leq 0.5</math> mg/mg, and
 
• eGFR <math>\geq 60</math> mL/min/1.73 m^2 or no confirmed decrease from baseline in eGFR of <math>>20\%</math>, and
 
• Received no rescue medication for LN (see Section 7.8, Prohibited Therapy and Concomitant Treatment), and
 
• Did not receive more than 10 mg prednisone for <math>\geq 3</math> consecutive days or for <math>\geq 7</math> days in total during Weeks 44 through 52, just prior to the renal response assessment.
 
 
Subjects who withdraw from the study prior to the Week 52 assessment will be defined as non responders.

Secondary Endpoints:
	
 
• Time to UPCR of <math>\leq 0.5</math> mg/mg.
 
• Partial renal response as defined by 50% reduction from baseline in UPCR at Weeks 24 and 52.
 
• Time to 50% reduction in UPCR from baseline.
 
• Renal response at Week 52 (based on definition of primary endpoint).
 
• Duration of UPCR <math>\leq 0.5</math> mg/mg.
 
• Proportion of subjects experiencing a confirmed <math>>30\%</math> decrease from baseline in eGFR at each timepoint.
 
• Change from baseline in UPCR at each time point.
 
• Change from baseline in serum creatinine, urine protein, and eGFR.
 

	
 
• Change from screening in immunology parameters (complement 3 (C3), C4, and anti-double-stranded DNA).
 
• Renal response with low-dose steroids (defined as renal response in the presence of corticosteroids of <math>\leq 2.5</math> mg between Weeks 16 to 24 and Weeks 44 to 52).
 
• Change from baseline in health-related quality of life at Weeks 12, 24, and 52.
 
• Health Resource Utilization at Weeks 24 and 52.
 
• Change from baseline in the Safety of Estrogens in Lupus Erythematosus National Assessment - Systemic Lupus Erythematosus Disease Activity (SELENA-SLEDAI) Index score at Weeks 24 and 52.
 

Procedures:	
See Schedule of Events for full details of protocol required procedures and applicable visits (and timings). Subjects who have provided signed and dated informed consent will be screened for entry into this study. Baseline proteinuria level is determined by a mean of 2 first morning void urine samples taken during the screening period. If a subject has not had a kidney biopsy within the required timeframe for study eligibility, one may be performed to assess eligibility into the study, provided consent is in place and provided the results are received before randomization. Subjects meeting the required eligibility criteria will be randomized in a ratio of 1:1 to receive either Orelvo (23.7 mg BID) or matching placebo starting on Day 1. All subjects will receive initial treatment with 0.5 to 1.0 g IV methylprednisolone. In consultation with the Medical Monitor, and if it is in the subject's best interest, IV methylprednisolone may be started during the screening period. Subjects receiving IV methylprednisolone in the 3 months prior to screening must be discussed with the Medical Monitor prior to initiating further IV methylprednisolone. For subjects who are not already taking prescribed MMF prior to randomization, the dosing of MMF will start at 500 mg BID for a total daily dose of 1 g/day for the first week, increasing to 1 g BID for a total daily dose of 2 g/day for the second and subsequent weeks (i.e., beginning on Day 8).
 
All subjects will complete dosing through 52 weeks of study treatment. Subjects who permanently discontinue study treatment before the Week 52 visit will return for all remaining study visits and assessments unless they have withdrawn consent. All subjects who complete participation and study treatment through 52 weeks and provide consent will have the opportunity to enroll into a continuation study for which the details are not yet finalized.

Sample Size:	
A 2 group continuity corrected Chi square test with a 0.05 two-sided significance level will have 80% power to detect the difference between a placebo response rate of 20.0% and an Orelvo response rate of 34.4% (odds ratio=2.1) when the sample size in each group is 162 (total N=324). While the effect of withdrawals will be investigated, subjects withdrawing for any reason will be counted as non-responders in the primary analysis and therefore no adjustment of sample size for withdrawals is necessary.

Statistical Methods:	
Analysis:
 
All statistical analyses will be undertaken at study closure and will incorporate all Week 24 and Week 52 endpoints.
 
Populations:
 
The efficacy analysis will be based on the intent-to-treat (ITT) principles and will consist of all randomized subjects.
 
The per-protocol set will be a subset of subjects in the ITT population who do not have any major protocol violations (to be defined prior to unblinding).
 
The safety analysis set will consist of all subjects who receive at least 1 dose of study treatment.
 
Methods:
 
The primary analysis of the primary endpoint, renal response at Week 52, will be conducted on the ITT population. The relative renal response for Orelvo compared to placebo will be determined using logistic regression. The logistic regression model will include terms for treatment, baseline UPCR, biopsy class, and MMF use at baseline. Results of this logistic regression will be displayed as odds ratios and a 2-sided confidence interval (CI) (Orelvo compared to placebo). The proportion of subjects exhibiting renal response at Weeks 24 and 52 will be summarized by treatment group.
 
The analyses of the secondary endpoints are described below:
 
Other binary endpoints will be analyzed in a similar manner to the primary endpoint. Endpoints measured as a time-to-event will be displayed using Kaplan-Meier methodology. Orelvo will be compared to placebo using a Cox proportional hazard model. The model will include terms for treatment and appropriate baseline assessments. Median time-to-event along with 2-sided CIs will be displayed.
 
Other endpoints will be summarized by visit and differences between baseline and on-treatment values at weeks up to and including Week 52 will be analyzed using Mixed Effect Model Repeated Measures (MMRM). The MMRM model will include terms for treatment, visit, treatment by visit interaction and baseline. Results will be expressed as differences between treatment arms (along with associated 95% CI).
 
Safety Endpoints:
 
Adverse events will be aggregated by System Organ Class and preferred term and presented as summary tables.
 
Laboratory values (based on results from the central laboratory), vital signs and other safety parameters will be summarized by visit as absolute values and change from baseline. Laboratory values outside of defined normal ranges will be summarized.
 
The impact of withdrawals on primary endpoint will be investigated with a tipping point analysis.

----------------------	---

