#### **1.2.4.2 Lupus Nephritis Clinical Development**

The AURA-LV study (Protocol AUR-VCS-2012-01) is a randomized, controlled, double-blind Phase 2 study comparing the efficacy and safety of voclosporin (23.7 mg BID or 39.5 mg BID) with placebo in achieving remission in patients with active LN. The duration of the study is 48 weeks and is ongoing. All patients received background therapy with MMF and corticosteroid taper. The primary endpoint of complete remission was defined as: urine protein creatinine ratio (UPCR) of  $\leq 0.5$  mg/mg at 24 weeks (using first morning void) and eGFR  $\geq 60$  mL/min/1.73 m^2 or no confirmed decrease from baseline in eGFR of  $\geq 20\%$ . In addition, patients could not receive rescue medications for LN (defined as  $>10$  mg prednisone/day for  $>3$  consecutive days or  $>7$  days total from Weeks 16-24) to be considered for complete remission.

A total of 265 subjects were randomized into the AURA-LV study. The 24-week primary endpoint assessment for the AURA-LV clinical study demonstrated that the groups were generally well balanced for age, gender and race, with a trend to higher proteinuria and lower eGFR data in the low-dose voclosporin arm. The low dose achieved a statistically significant benefit over placebo for the primary efficacy assessment of complete remission at 24 weeks (odds ratio (OR) [95% CI] = 2.03, [1.01, 4.05],  $p=0.045$ ), without a statistically significant improvement seen in the high dose. The results were confirmed by 24 hour urine collections ( $p=0.047$ ). Both the low- and high-dose voclosporin were statistically superior to placebo in partial remission, time to complete remission, and time to partial remission. A mean reduction in serum creatinine was seen in both arms (0.2 mg/dL low, 0.1 high;  $p<0.001$ ). In the voclosporin groups, eGFR fell by a median of 8-9 mL/min by Week 4 and then stabilized over the course of the study. Blood pressure did not vary by group. The correlation of 24-hour urine protein and using the first morning void was assessed from the results of the AURA-LV study demonstrating a high degree of correlation (Pearson Correlation Coefficient = 0.92).

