### 13.2 Sample Size and Power Calculations

The total sample size will be 324 subjects (162 subjects per treatment arm). This is based on the following assumptions:

- A two group continuity corrected Chi square test with a 0.05 two-sided significance level will have 80% power to detect the difference between a placebo response rate of 20.0% and a Orelvo response rate of 34.4% (odds ratio=2.1) when the sample size in each group is 162 (total N=324).
- The effect of withdrawals will be investigated. Subjects withdrawing for any reason will be counted as non-responders in the primary analysis and therefore no adjustment of sample size for withdrawals is necessary.
- The impact of withdrawals on primary endpoint will be investigated with a tipping point analysis.

Table 3 shows the Orelvo response rates required to maintain a minimum 80% power at the planned sample size for given placebo response rates. These response rates all lead to odds ratios of around 2, which is a clinically relevant effect.

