## 13.8 Statistical and Analytical Methods

### 13.8.1 Primary Efficacy Analysis

The primary efficacy endpoint is the renal response at Week 52 (Section 13.7.1, [Primary Endpoint](#)).

The study null hypothesis  $H_0$  and alternative hypothesis  $H_1$  are as follows:

$H_0$ : There is no difference in renal response between Orelvo and placebo.

$H_1$ : There is a difference in renal response between Orelvo and placebo.

The null hypothesis  $H_0$  will be rejected in favor of  $H_1$  if there is evidence at the 5% significance level using a 2-sided test.

The primary efficacy analysis will be conducted on the ITT set using logistic regression with terms for treatment, baseline UPCR, biopsy class, and MMF use at baseline. The results being expressed as an odds ratio (and associated two-sided 95% CI) for Orelvo compared to placebo. Odds ratios greater than unity show the odds of response are greater for Orelvo than for placebo and therefore indicate a benefit of the Orelvo treatment arm.

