### 6.11.1 Primary Endpoint

The primary endpoint is the number of subjects showing renal response at 52 weeks. Renal response at Week 52 will be adjudicated by the CEC based on the following parameters:

- UPCR of  $\leq 0.5$  mg/mg, and
- eGFR  $\geq 60$  mL/min/1.73 m^2 or no confirmed decrease from baseline in eGFR of  $>20\%$ , and
- Received no rescue medication for LN, and
- Did not receive more than 10 mg prednisone for  $\geq 3$  consecutive days or for  $\geq 7$  days in total during Weeks 44 through 52, just prior to the renal response assessment

The CEC will be blind to treatment group and completely independent of Aurinia. They will also take into consideration the following:

- Subjects who withdraw from the study prior to the Week 52 assessment and thus provide insufficient Week 52 data will be defined as non-responders
- Medication listings will be reviewed by the CEC as part of the adjudication process. The CEC will have complete autonomy to adjudicate any treatment as rescue medication. However, as any dose of MMF is permitted within this protocol there is no MMF dose level that necessarily classifies it as being rescue medication. As part of this review the CEC will also adjudicate on steroid drug use beyond the protocolled taper.

- eGFR values eliminating a subject from complete remission should be accompanied by a treatment or disease-related TEAE that impacts eGFR. To this end, eGFR measures which would ordinarily result in a subject not being in remission will only be used if the first eGFR assessment occurs on a date where there is also a treatment or disease-related, eGFR associated TEAE. The following is a list of MedDRA preferred terms that are associated with eGFR decreases:
  - BLOOD CREATININE INCREASED
  - CREATININE RENAL CLEARANCE DECREASED
  - GLOMERULAR FILTRATION RATE DECREASED
  - SERUM CREATININE INCREASED
  - RENAL IMPAIRMENT
  - RENAL FAILURE
  - RENAL FAILURE ACUTE
- Confirmation of eGFR decreases from baseline require that two consecutive measures at least 3 days apart exhibit the decrease.

The null hypothesis  $H_0$  will be rejected in favor of  $H_1$  if there is evidence at the 5% significance level using a 2-sided test.

$H_0$ : There is no statistically significant difference in renal response between voclosporin and placebo at Week 52

$H_1$ : There is a statistically significant difference in renal response between voclosporin and placebo at Week 52.

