## 6.11.2 Primary Efficacy Analysis

### 6.11.2.1 Renal response at Week 52

Renal response at Week 52 will be adjudicated by the Clinical Endpoints Committee (CEC) and as such the analysis will incorporate the CEC's assessments of each subject. In order to perform their adjudication, the CEC will be provided UPCR data, eGFR data, steroid taper data, rescue and prohibited medication data and adverse event data. Full details of the adjudication process are detailed in a separate CEC Charter.

The primary efficacy analysis will be conducted on the ITT population using a logistic regression model with terms for treatment, baseline UPCR, biopsy class, MMF use at baseline and region, and renal response (Yes/No) at week 52 as the response variable (Table 14.2.1.1.2).

The results will be expressed as an odds ratio (and associated two sided- 95% CI) for voclosporin compared to placebo. Odds ratios greater than unity will mean the odds of response are greater for voclosporin than for placebo and therefore indicate a benefit of the voclosporin treatment arm. The p-value of the treatment effect will also be reported.

The following SAS program will be used for the primary efficacy analysis:

```
Proc Logistic data = data;  
Class Treatment_arm MMF_Use Biopsy_Class Region;  
Model Response = Treatment_arm MMF_Use Biopsy_Class Baseline_UPCR Region;  
Run;
```

The number of responders and non-responders at Week 52 will be summarized by treatment arm and a listing of renal responders and non-responders will also be provided.

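### The primary logistic model adjusts for baseline UPCR but not baseline eGFR, and no planned sensitivity model fills the gap; a small robustness point, not a bias of the design

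*Protocol*

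**What the plan says.** The protocol synopsis describes the primary analysis as follows: "The logistic regression model will include terms for treatment, baseline UPCR, biopsy class, and MMF use at baseline". Protocol 13.8.1 specifies "logistic regression with terms for treatment, baseline UPCR, biopsy class, and MMF use at baseline", which matches the synopsis. SAP 6.11.2.1 specifies a "logistic regression model with terms for treatment, baseline UPCR, biopsy class, MMF use at baseline and region", and SAP 9 explains that region was added after regulatory feedback.

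The endpoint (Protocol 3.3.1; SAP 6.11.1) needs UPCR at or below 0.5 mg/mg. It also needs an eGFR that is either at least 60 or not confirmed to have fallen by more than 20% from baseline. There are further conditions on rescue medication and steroids. SAP 6.11.1 qualifies the eGFR part: "eGFR values eliminating a subject from complete remission should be accompanied by a treatment or disease-related TEAE that impacts eGFR".

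Baseline eGFR is available for every subject. Protocol 7.6.1 requires at least two pre-dose values, and SAP 6.2.2 defines baseline as the lowest of them. It is not used in:

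- the randomisation, which is stratified by biopsy class and prior MMF use and blocked by region (SAP 5);
- the sensitivity models of SAP 6.11.2.2, which use treatment alone, the model without region, and then age, gender, race, biopsy class, region, MMF use and maximum MMF dose in turn;
- the imputation and analysis models of the tipping-point analysis (SAP 6.11.2.4).

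SAP 6.6 summarises it descriptively by arm.

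On Phase 2, Protocol 1.2.4.2 reports groups that were generally well balanced for age, gender and race, but "with a trend to higher proteinuria and lower eGFR data in the low-dose voclosporin arm". No figures are given.

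**The concern.** The plan adjusts for the baseline of one laboratory component of the endpoint and not the other. Baseline eGFR could matter in two ways. It may be a general marker of how likely a subject is to respond. It also enters the endpoint definition: because an eGFR of at least 60 passes whatever the change, the fall needed to fail depends on where the subject started.

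The stakes are modest. If baseline eGFR predicts response after allowing for UPCR, leaving it out gives away a little precision on average. It also leaves the primary estimate exposed to whatever eGFR imbalance happens to occur. The baseline table would show such an imbalance, but no planned analysis of the primary endpoint would correct for it. Adjustment added after seeing the data would carry less weight, whichever arm it favoured.

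**Working it through.** **1. The plan's own figure.** Protocol 13.2: 20.0% v 34.4%, 162 per arm, two-sided 0.05, continuity-corrected chi-square. With p̄ = 0.272:

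- z = [0.144 − 1/162 − 1.96·√(2·0.272·0.728/162)] / √[(0.2·0.8 + 0.344·0.656)/162] = (0.1378 − 0.0969)/0.0488 = 0.84
- Power = Φ(0.84) = 79.9%. The sample-size formula gives 163 per arm, and the odds ratio is (0.344/0.656)/(0.2/0.8) = 2.10.

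The stated design reproduces. It rests on an unadjusted test, so it does not depend on any covariate.

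**2. How the definition links baseline to response.** Before the SAP's adverse-event condition, the fall needed to fail is max(20%, 1 − 60/baseline):

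- baseline 75 or below: just over 20%;
- baseline 100: more than 1 − 60/100 = 40%;
- baseline 120: more than 1 − 60/120 = 50%.

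The Phase 2 median fall of 8–9 mL/min (Protocol 1.2.4.2) is 16–18% from a baseline of 50 and 11–12% from 75, so the typical fall stays under the limit.

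The definition alone is unlikely to create a strong predictor. Suppose 30% respond in the upper half of baseline eGFR, and a fraction f of responders in the lower half is lost to the eGFR component. The half means of a normal variable differ by 1.60 SD. The odds ratio per SD is then exp{ln[(0.3/0.7)/(p/(1−p))]/1.60} with p = 0.3(1−f).

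- f = 10%: p = 0.27, about 1.10 per SD.
- f = 30%: p = 0.21, about 1.35 per SD.
- f = 53%: p = 0.141, about 1.82 per SD.

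Values of 1.5 to 2.0 therefore need baseline eGFR to be prognostic for other reasons too. The documents give no figure, so the range below is an assumption.

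**3. How often an imbalance arises.** The SD of the between-arm difference in a standardised covariate is √(2/162) = 0.111. An imbalance of 0.2 SD is 0.2/0.111 = 1.8 standard errors, so at least this much against the drug has probability 3.6%, and in either direction about 7%.

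**4. Simulation A.** 162 per arm, 6,000 trials per setting, marginal rates fixed at 20.0% and 34.4%. Wald test for treatment alone v treatment plus a standard normal covariate standing for baseline eGFR; other covariates were left out of both models. The right-hand columns take trials with an imbalance worse than −0.15 SD (mean −0.20; 8–10% of trials).

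| Assumed OR per SD | Average power, without v with | Power given imbalance, without v with | Estimated OR given imbalance, without v with |
|---|---|---|---|
| 1.0 | 82.4% v 82.6% | 81% v 81% | 2.12 v 2.12 |
| 1.2 | 82.0% v 82.0% | 81% v 85% | 2.05 v 2.14 |
| 1.5 | 84.4% v 85.4% | 72% v 82% | 1.91 v 2.13 |
| 2.0 | 83.8% v 86.3% | 68% v 86% | 1.85 v 2.26 |

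Under the null, rejection was 5.1–5.7% without the covariate and 5.2–5.5% with it. The right-hand subsets hold only about 500 trials, so each power there has a standard error of about √(0.72·0.28/480) = 2 points.

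**5. Hand check.** The SE of the log odds ratio is √[1/(162·0.16) + 1/(162·0.2257)] = 0.257. Power without imbalance is about Φ(ln 2.10/0.257 − 1.96) = Φ(0.92), or 82%. A −0.2 SD imbalance shifts the log odds ratio by about −0.2·ln(OR per SD).

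- OR 1.5: shift −0.081 = −0.32 SE, power Φ(0.61) = 73%.
- OR 2.0: shift −0.139 = −0.54 SE, power Φ(0.38) = 65%.

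Both agree with the table within simulation error.

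**6. Simulation B.** 4,000 trials per setting, with baseline UPCR in both models. The average gain was 0.2 to 1.3 points. With the imbalance fixed at −0.2 SD, power without v with eGFR was 78.7% v 84.8% (OR 1.35 per SD), 77.1% v 85.1% (1.49) and 72.3% v 86.2% (1.82). Having UPCR in the model does not remove the effect.

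**The case against.** The strongest reply is that covariate choice is discretionary and this plan already adjusts for every randomisation factor plus baseline UPCR. Nothing it states is wrong and its error rate is controlled. All of that stands.

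The SAP also weakens the link with eGFR. A low value disqualifies only when the fall is confirmed at least 3 days apart and the first low value coincides with a related eGFR-type adverse event. SAP 6.11.2.3 counts a confirmed fall to below 60 without such an event as eGFR success. Taking the lowest pre-dose value as baseline makes a 20% fall harder to reach. This stands too, and is why the endpoint definition cannot by itself justify a large assumed effect.

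Two stronger readings are tempting. A reader might infer that omitting eGFR biases the odds ratio. It does not: the expected imbalance under randomisation is zero, and a shift given one realised imbalance is equally likely in either direction. Part of the gap between the two odds ratios is also non-collapsibility, since the marginal value is 2.10 and the conditional value 2.10 to 2.24 over the assumed range.

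A reader might also infer from Phase 2 that the voclosporin arm will again start with lower eGFR. An unquantified trend in a separate randomisation shows only that such a difference can occur; it says nothing about direction here.

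What the reply does not answer is that an imbalance visible in the baseline table would have no pre-specified adjusted analysis of the primary endpoint. Tabulating eGFR success by arm (SAP 6.11.2.3) does not supply one.

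**Conclusion.** The omission is confirmed in the primary, sensitivity and tipping-point models. It is a limited weakness in precision and robustness. It does not invalidate the primary test, whose type I error stays at about 5%, and it does not disturb the sample-size calculation.

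On average the cost is about 0 to 2.5 points of power for assumed odds ratios of 1.0 to 2.0 per SD, and effectively nothing if eGFR is weakly prognostic. The larger loss, about 10 to 18 points relative to the adjusted analysis, needs two things together: an adverse imbalance of about 0.2 SD and an odds ratio of 1.5 to 2.0 per SD beyond the existing covariates. The first is uncommon. The second is an assumption that the documents neither support nor exclude. A favourable imbalance would flatter the drug in the same way.

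**What to change.** Before unblinding, add baseline eGFR, as defined in SAP 6.2.2, as a continuous covariate to the primary model in SAP 6.11.2.1. Make the same addition to the imputation and analysis models in SAP 6.11.2.4, which are meant to mirror the primary covariates. Keep the current model as a sensitivity analysis in SAP 6.11.2.2, and record the departure from Protocol 13.8.1 in SAP 9, as was done for region.

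If the sponsor prefers to leave the primary model alone, the minimum is to pre-specify in SAP 6.11.2.2 the primary model plus baseline eGFR. That would answer the question of a chance imbalance without post hoc choice.

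The cost is wording, one degree of freedom, and an odds ratio conditional on one more covariate, which makes it slightly less comparable with the Phase 2 odds ratio. No new data are needed.
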